16.9	Appendix I: Cockcroft-Gault Creatinine Clearance Calculation	55
17.	References.....	56

TABLE OF CONTENTS	Page
Figure 1. CD34+ Chimerism cells	20
Figure 2. Conventional and CD34+ donor chimerism monitoring in patients with (left column) and without (right column) hematologic relapse	20
Figure 3. Chemical Structure of Lenalidomide.....	23
Figure 4. Dose Limiting Toxicity Flow Diagram	27

ABBREVIATIONS

AE	Adverse Event
aGVHD	Acute Graft-Versus-Host-Disease
ALT	Alanine Transaminase (also SGPT)
AML	Acute Myelogenous Leukemia
ANC	Absolute Neutrophil Count
AST	Aspartate Transaminase (also SGOT)
AUC	Area Under Curve
AUC _(0-t)	Area Under the Plasma Concentration-time curve from time zero to time t
AUC _(0-∞)	Area Under the Plasma Concentration-time curve from time zero to infinity
AUC _(0-Tlast)	Area Under the Plasma Concentration-time curve from time zero to the last measurable time point
BUN	Blood Urea Nitrogen
CBC	Complete Blood Count
CIBMTR	Center for International Blood and Marrow Transplant Research
C _{max}	Maximum Plasma Concentration
CR	Complete Remission
CRF	Case Report Form
CTCAE	Common Terminology Criteria for Adverse Events
DFS	Disease-free Survival
DLT	Dose-Limiting Toxicity
DNA	Deoxyribonucleic Acid
DISC	Data Integrity and Safety Committee

eCRF	Electronic Case Report Form
FCBP	Female of Child-Bearing Potential
FDA	Food and Drug Administration
GCP	Good Clinical Practice
GVHD	Graft-Versus-Host-Disease
GVL	Graft-Versus-Leukemia
HCT	Hematopoietic Cell Transplant
HI	Hematologic Improvement (see Appendix D)
ICH	International Conference on Harmonization
IND	Investigational New Drug
IP	Investigational Product
IPSS	International Prognostic Scoring System
IRB	Institutional Review Board
IWG	International Working Group
MDS	Myelodysplastic syndromes
MG	Milligram
MRD	Minimal Residual Disease
MTD	Maximum Tolerated Dose
NIH	National Institutes of Health
NK	Natural Killer
OS	Overall Survival
PD	Pharmacodynamics

PI	Principal investigator
PML	Promyelocytic Leukemia
PO	By Mouth
PR	Partial Remission
QD	Every Day
QOD	Every Other Day
RBC	Red Blood Cells
REMS	Risk Evaluation and Mitigation Strategy
SAE	Serious Adverse Event
SD	Stable Disease
SGOT	Serum Glutamic Oxaloacetic Transaminase (also AST)
SGPT	Serum Glutamic Pyruvate Transaminase (also ALT)
SPM	Second Primary Malignancy
STR	Short Tandem Repeat
UFHCC	University of Florida Health Cancer Center
US	United States
WBC	White Blood Cell
WHO	World Health Organization

PROTOCOL SYNOPSIS

Title:	A phase I clinical trial to evaluate the maximally tolerated dose (MTD), dose limiting toxicities (DLTs) and safety profiles of escalating doses of lenalidomide after allo-HCT in AML and MDS subjects with minimal residual disease (MRD) detected by the CD34+ mixed chimerism analysis
Rationale:	
Prognosis of high risk AML and MDS remains poor and less than 30% of these patients achieve long term survival. Allogeneic transplant (allo-HCT) is an effective therapy for high risk AML and MDS, however, post-transplant disease relapse continues to be a major obstacle to treatment success and cure. Therefore, there is an urgent need to develop novel therapeutic strategies to effectively prevent disease relapse in AML and MDS patients after allo-HCT.
 
This phase I clinical trial is designed to evaluate the maximally tolerated dose (MTD), dose limiting toxicities (DLTs) and safety profiles of increasing doses of lenalidomide after allo-HCT in AML and MDS subjects with minimal residual disease (MRD) detected by the CD34+ mixed chimerism analysis.
 
Lenalidomide has a potent immunomodulatory activity and is capable of activating T- and natural killer (NK)-cells. T- and NK-cells mediated immunity plays a critical role in host defense against progression of myeloid malignances, therefore restoration of impaired cytotoxic activity of T- and NK cells with lenalidomide could have significant clinical implications in patients with relapsing MDS and AML after allo-HCT because alloreactive T- and NK-cells play a crucial role in the GVL effect, which is considered to be a key mechanism preventing disease relapse after allo-HCT. Treatment of relapsed disease is more successful if initiated early when tumor burden is minimal. Previous studies evaluating the role of lenalidomide in patients with relapsed myeloid malignances showed its efficacy only in patients with low blast count. For this purpose, monitoring of MRD allows timely therapeutic interventions before the hematologic relapse becomes clinically apparent and while tumor burden is minimal. However, in AML and MDS patients monitoring of MRD is technically difficult and is not routinely implemented in clinical practice. For these purposes, new approaches for MRD detection are currently being explored.
 
Lineage-specific chimerism analysis of CD34+ cells is a novel approach, which has better sensitivity and specificity for early MRD detection after allo-HCT. It was demonstrated that monitoring of CD34+ chimerism in patients with AML and MDS after allo-HCT is a very sensitive technique, which is capable to early identify patients at a very high risk for a hematologic relapse. Our preliminary data showed that of 10 enrolled patients 4 patients had hematologic relapse confirmed by a bone marrow


	
evaluation. In each patient with relapsed disease there was a significant decline in CD34+ specific chimerism, which was detected for at least a month prior to confirmed hematologic relapse. The CD34+ specific STR analysis is superior to conventional chimerism analysis for MRD monitoring and identification of early relapse after allo-HCT. More importantly, drop of CD34+ specific chimerism occurred significantly earlier than decrease in chimerism assessed by conventional STR-based techniques. Therefore, the use of highly sensitive and specific MRD monitoring by the CD34+ chimerism analysis substantially increases the reliability of early MRD detection after allo-HCT allowing early therapeutic interventions and is potentially practice changing.
 
Therefore, the proposed research project is highly significant because it seeks to develop a novel therapeutic strategy to effectively delay or prevent AML and MDS relapse in allo-HCT recipients. Successful completion of this phase I study will build the foundation for a subsequent phase II trial of pre-emptive lenalidomide administration to prevent or delay an imminent hematological relapse after allo- HCT in subjects with MDS and AML with minimal residual disease (MRD) detected by the CD34+ mixed chimerism analysis, which would likely impact the clinical care of allo-HCT recipients with high risk AML and MDS and will give valuable insights into mechanisms of action of lenalidomide after allo-HCT.

Primary Objective:
	
To determine safety and the maximum tolerated dose of lenalidomide after allo-HCT in AML and MDS subjects with MRD detected by the CD34+ mixed chimerism analysis.

Secondary Objective:
	
To monitor changes in the CD34+ mixed chimerism after allo-HCT in AML and MDS subjects with detectable MRD in response to escalating doses of lenalidomide.


Study Design:
	
This is an open-label, phase I dose escalation study of lenalidomide after allo-HCT in AML and MDS subjects with MRD detected by the CD34+ mixed chimerism analysis. The study is designed to evaluate the safety profile, MTD and biologic activity of lenalidomide after allo-HCT in patients with AML and MDS
 
The dose levels of lenalidomide will be as follows:
 
Dose Level 1: 2.5 mg PO QOD Day 1-21 for 28 day cycle X 2 cycles Dose Level 2: 2.5 mg PO QD Day 1-21 for 28 day cycle X 2 cycles Dose Level 3: 5 mg PO QD Day 1-21 for 28 day cycle X 2 cycles Dose Level 4: 7.5 mg PO QD Day 1-21 for 28 day cycle X 2 cycles
 
Subjects will be enrolled in cohorts of three (3). Lenalidomide will be administered for 21 consecutive days in a 28 day cycle X 2 cycles. The starting dose will be 2.5 mg given orally every other day for 21 days.

Subjects will be individually assessed for safety and dose limiting toxicity (DLT) for the purpose of determining the MTD .Three eligible subjects will be enrolled in sequential cohorts at increasing dose levels until at least one DLT is seen between the first dose and 14 days after the last dose of lenalidomide. For this study, MTD will be defined as the highest dose which no more than 34% of the subjects observed at a given dose level experience a DLT. The following dose escalation rules will be used and applied:

1. Three subjects are initially studied at each dose level.
2. If none of these 3 subjects experience DLT, then the dose is escalated to the next dose level in 3 subsequent subjects.
3. If 1 of these 3 subjects experiences DLT at current dose, then up to 3 more subjects are accrued at the same level.
 - a) If none of these 3 additional subjects experience DLT, then the dose is escalated to the next dose level in 3 subsequent subjects.
 - b) If 1 or more of these 3 additional subjects experiences DLT, then the MTD is considered to have been exceeded and the previous dose level will be the MTD.
4. If 2 or more of the initial 3 subjects at a dose level experience DLT, then the MTD is considered to have been exceeded and dose escalation will be stopped. Up to 3 more subjects are treated at the next lower dose.

A subject must meet one of the following 3 criteria to be evaluable for subsequent dose-escalation decisions:

1. Complete at least 21 days of lenalidomide without a DLT by 14 days after the last dose of lenalidomide;
2. Experienced a DLT between the first dose and 14 days after the last dose of lenalidomide; or
3. Withdrawn from the study after at least 14 days of lenalidomide administration.

If a subject does not meet any of these criteria, the subject is not evaluable for dose escalation decisions and will be replaced in that cohort. No more than 3 subjects will be added simultaneously to a dose cohort during dose escalation.

The study ends when there is a maximum dose where 2 or more subjects out of 6 have a DLT, or when the maximum sample size of twenty four (24) subjects has been reached.

Dose Limiting Toxicity

DLT will be defined as any of the following adverse events that are not clearly unrelated to drug administration or treatment-emergent from lenalidomide and constitute a change from baseline irrespective of outcome. For the purpose of dose-escalation decisions and MTD

	
determination, only DLTs that occur within 14 days after the last dose of lenalidomide administration will be taken into account.
 
 1. Grade 3 or greater nausea, diarrhea, or vomiting despite the use of maximal medical intervention; 2. Grade 3 or greater acute GVHD despite the use of maximal medical intervention; 3. Any other clinically significant non-hematologic toxicity of grade 3 or greater considered not related to the underlying disease or intercurrent illness; 4. Grade 3 or greater neutropenia; 5. Grade 4 thrombocytopenia or platelet count ≤ 50 thou/mm³ by day 28 of lenalidomide administration; or 6. Any treatment-related effect leading to a subject missing 3 or more doses of lenalidomide. 
Correlative Studies:
 
Peripheral blood will be collected to examine the CD34+ specific chimerism.


Inclusion/ Exclusion Criteria:
	
Inclusion Criteria:
 
 1. Subjects must be at least 18 years of age; 2. Subjects must be 60 (+/- 7) days post-allogeneic transplant from any donor source; 3. Subjects must have either: 
 a) High risk CD34+ AML (de novo or secondary, and any WHO 2008 classification excluding acute promyelocytic leukemia, see Appendix A). High risk AML is defined as (a) disease status beyond complete remission (CR) #1 at transplant or (b) treatment related AML or (c) presence of adverse cytogenetics including inv(3); t(3;3); t(6;9); t(v;11); -5 or del(5q); -7; abn(17p) or complex karyotype; or b) High risk CD34+ MDS (WHO 2008 classification, see Appendix B). High risk is defined as (a) blast count $\geq 5\%$ at the time of transplant or (b) treatment related MD or (c) presence of adverse cytogenetics including -7/del7q or complex karyotype; 4. For AML subjects, they must have a documented CR within 45 days prior to allo-HCT; 5. For MDS subjects, they must have $< 20\%$ myeloblasts in the bone marrow within 45 days prior to allo-HCT; 6. Subject Karnofsky performance status must be ≥ 70; 7. Subjects must be platelet transfusion independent (Platelet transfusion independence is defined as 7 days or greater without a platelet transfusion); 8. Neutrophil count ≥ 1.0 thou/mm³ and platelet count ≥ 30 thou/mm³;

	
9. Subjects must have total bilirubin ≤ 2 mg/dL;
 
10. Subjects must have serum AST and ALT levels ≤ 2.5 times upper limit of normal;
 
11. Subjects must have serum creatinine < 2.5 times upper limit of normal and a calculated creatinine clearance ≥ 30 ml/min by Cockcroft-Gault formula (see Appendix I: Cockcroft-Gault Creatinine Clearance Calculation);
 
12. All study participants who will receive lenalidomide based on the CD34+ chimerism testing must be registered into the mandatory Revlimid REMS[®] program, and be willing and able to comply with the requirements of the REMS[®] program;
 
13. Females of child-bearing potential (i.e., women who are premenopausal or not surgically sterile) may participate, provided they meet the following conditions:
 
a) Females of reproductive potential must adhere to the scheduled pregnancy testing as required in the Revlimid REMS[®] program; and
 
14. Written, voluntary informed consent, willingness, and ability to comply with all study procedures.
 
Exclusion Criteria:
 
 1. CD34- AML or MDS; 2. Subjects with peripheral blasts or progressive cytopenias will be excluded unless a CR or CRi confirmed by a bone marrow biopsy within two weeks post of the allo-HCT; 3. Inability to give informed consent; 4. Uncontrolled active infection(s) requiring intravenous antibiotics; 5. Known or suspected hypersensitivity to lenalidomide; 6. Grade II-IV acute GVHD or extensive GVHD; 7. Not able to swallow the lenalidomide capsule as a whole; or 8. Female subjects who are pregnant or nursing;

Accrual:
	
The sample size for the study is based on incidence of DLT; however, it is not to exceed 24 subjects. The accrual period will be three years.

Study Duration and Dates:
	
The subject recruitment period is approximately 36 months, starting last quarter 2015. The study duration encompasses the following:
 
 • Screening period of up to 14 days (+/-7 days from Day +60); and • The CD34+ donor chimerism will be performed on days +60 and +90 (± 7 days) post-transplant until the CD34+ donor chimerism drops to $\leq 90\%$. If the CD34+ donor chimerism continues to be $> 90\%$ by day +90 (± 7 days) post-transplant the patient will be removed from the study; • Treatment with lenalidomide will start within 10 days after detection of the CD34+ donor chimerism $\leq 90\%$ and be continued

	
for 21 days in a 28 day cycle X 2 cycles or until terminating event occurs;
 
 In subjects receiving lenalidomide, the CD34+ donor chimerism will be performed at Days +60 and +120 (± 7 days) of lenalidomide therapy.
Safety Assessments:	
Subjects will be examined weekly per institutional standard of care. Examinations will consist of vital sign measurements, physical examinations, laboratory assessments (hematology, serum chemistries) and assessment of acute GVHD. NCI Common Terminology Criteria for Adverse Events (CTCAE), Version 4.0 will be used to grade toxicity and adverse events.
 
GVHD assessment: Acute GVHD will be evaluated as per institutional practice guidelines using established staging criteria (see Appendix F). GVHD severity will be determined clinically; however, biopsies of affected organs are encouraged whenever possible. GVHD assessments will be performed at screening and Days +60 & +90. If lenalidomide is initiated, GVHD assessments will be performed weekly during scheduled visits and continuing until 30 days after the last dose of lenalidomide. GVHD assessments will also be documented at Days +60 and Day +120 after the initiation of lenalidomide.
 
Overall grading and response to GVHD therapy will be measured through the use of the consensus and IBMTR GVHD severity indices based on physical exam and laboratory serum values (see Appendix F). Individual organ stages will be scored by the attending physician or other trained provider.

Immunosuppression:	All patients should receive standard GVHD prophylaxis per institutional guidelines per the treating physician.
Efficacy Assessments:	The efficacy outcome of interest will be reversal of the decreased CD34+ specific donor chimerism by day 60 of lenalidomide administration.
Statistical Procedures:	This study is descriptive in nature and not designed to provide analytical inferential results regarding primary or secondary endpoints. The sample size is based primarily on clinical considerations and not on statistical power calculations. Statistical characteristics of the “3 + 3” design are described in Appendix G. Descriptive statistics will be used to summarize baseline subject characteristics, treatment administration, and safety variables. All subjects who receive at least 5 doses of lenalidomide and have one post-dose safety assessment will comprise the safety population. The efficacy evaluable population will comprise all subjects who complete

	at least 15 days of lenalidomide and have at least one post-therapy CD34+ specific chimerism assessment.
--	--

Schedule of Events

Assessment	Screening (+/-7 days from Day +60)	Post- Transplant Monitoring Days +60 & 90 (\pm 7 days)	Revlimid C1D1, C2D1	End of Treatment 30 Days post- last Revlimid Dose (\pm 2 days)	Post- Revlimid Monitoring Days +60 & +120 (\pm 7 days)	Survival Every 3-months for 1 year
Signed Informed Consent	X					
Demographics, Medical /Treatment History	X					
MDS and AML WHO Classification	X					
Weight, Height	X					
Physical Examination	X	X	X	X	X	
GVHD Assessment ^A	X	X	X	X	X	
Vital Signs	X	X	X	X	X	
Karnofsky Performance Score	X	X	X	X	X	
CBC + Differential	X	X	X	X	X	
Serum Chemistry	X	X	X	X	X	
Serum Pregnancy Test (females) ^B	X		X			
Bone Marrow Aspiration and Biopsy ^C	X					
Peripheral Blood Chimerism		X				
Peripheral blood CD34+ donor chimerism ^D		X			X	
Dispense Revlimid (21-day supply)			X			
Concomitant Medications	X	X	X	X		
Adverse Events Assessments	X	X	X	X		
Concomitant Blood Products	X	X	X	X		
Disease Response Assessment ^C	X	X				X
Survival Assessment				X		X

- A. Overall grading and response to GVHD therapy will be measured through the use of the consensus and IBMTR GVHD severity indices. GVHD assessments will be performed at screening and Days +60 & +90. If lenalidomide is initiated, GVHD assessments will be performed weekly during scheduled visits and continuing until 30 days after the last dose of lenalidomide. GVHD assessments will also be documented at Days +60, and Day +120 after the initiation of lenalidomide.
- B. Females of reproductive potential must have 2 negative pregnancy tests prior to initiating therapy. The first test should be performed within 10-14 days, and the second test within 24 hours prior to prescribing REVLIMID therapy and then weekly during the first month, then monthly thereafter in women with regular menstrual cycles or every 2 weeks in women with irregular menstrual cycles.
- C. All disease assessments which occur during routine care of the subject will be recorded in the CRF. Bone marrow procedures or other disease assessments will be performed according to institutional guidelines or physician discretion.
- D. The peripheral blood CD34+ donor chimerism will be performed on days +60 and +90 (\pm 7 days) post-transplant until the CD34+ donor chimerism drops to \leq 90%. In subjects receiving lenalidomide, the CD34+ donor chimerism will be performed at Days +60 and +120 (\pm 7 days) of lenalidomide therapy. Additional CD34+ donor chimerism testing will be performed at the discretion of the clinical investigator (e.g., when a subject develops peripheral blasts, worsening pancytopenia, or extramedullary relapse).

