11.2 Replacement of Subjects

Subjects who are withdrawn prior to completion of 21 days of lenalidomide for any reason will be replaced.

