13.2 Analysis Populations

13.2.1 Safety Population

The safety population will consist of all subjects who received at least one dose of study drug and had at least one post-dose safety assessment. Safety summaries will include all subjects in the safety population.

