13.2.2 Dose Limiting Toxicity Evaluable Population

A subject is evaluable in dose-escalation decisions provided the subject has received at least five doses without a DLT, has experienced a DLT, or has been withdrawn from the study prior to completing of 21 days of lenalidomide due to a DLT. If a subject withdraws from the study without meeting these criteria, the subject will be replaced in that cohort. Tabulations of DLTs will only include the DLT-evaluable population.

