13.3 Analysis Methods

13.3.1 Safety

Safety evaluation will include monitoring for adverse events, scheduled laboratory assessments, vital sign measurements, and physical examinations. The intensity of adverse changes in physical signs or symptoms will be graded according to the CTCAE version 4. For all other adverse events not listed in the CTCAE, the intensity of these events will be assessed by the Investigator using a 5-point scale as described in Section 10.3.2.

The number of adverse events and the incidence of adverse events will be summarized. Adverse events will be summarized by maximum intensity (as described in Section 10.3.2) and relationship to study drug for each treatment group. Separate summaries will be provided for all adverse events, serious adverse events, treatment-related adverse events, and other significant adverse events (*e.g.*, adverse events leading to study discontinuation).

Clinical laboratory results will be listed by subject or, as appropriate, summarized descriptively by treatment group, which will include a display of change from baseline. Laboratory values outside of the normal ranges will be identified. Clinically significant hematologic laboratory abnormalities (*i.e.*, meet Grade 3, 4, or 5 criteria according to CTCAE v.4) will be listed and summarized.

Physical examination, vital sign, and GVHD data will be listed for each subject at each study visit. If appropriate, descriptive statistics for vital signs, both observed values and changes from baseline, will be summarized by treatment group.

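### The synopsis requires five doses for the safety population and Section 13.2.1 requires one; under the synopsis rule the AE and SAE summaries omit subjects who stop after 1 to 4 doses

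*Combined protocol and SAP*

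**What the plan says.** The safety population is defined twice.

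- **Protocol Synopsis, Statistical Procedures:** "All subjects who receive at least 5 doses of lenalidomide and have one post-dose safety assessment will comprise the safety population".
- **Section 13.2.1:** the population is "all subjects who received at least one dose of study drug and had at least one post-dose safety assessment". The section adds: "Safety summaries will include all subjects in the safety population".

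Section 13.3.1 lists the summaries concerned: all AEs, SAEs, treatment-related AEs, and other significant AEs, with "adverse events leading to study discontinuation" as the example of the last group. AEs are to be summarised by treatment group.

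Two other provisions bear on subjects who stop early. Section 11.2 says: "Subjects who are withdrawn prior to completion of 21 days of lenalidomide for any reason will be replaced". Section 13.2.2 defines a separate DLT-evaluable set, which keeps any subject with a DLT and otherwise needs at least five doses. It adds: "If a subject withdraws from the study without meeting these criteria, the subject will be replaced in that cohort". It also says: "Tabulations of DLTs will only include the DLT-evaluable population".

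**The concern.** The two definitions differ by exactly one group: subjects who took 1 to 4 doses and had a post-dose safety assessment. Those who stop treatment within days of starting may have stopped because of an adverse event, so a safety population should not lose them without a stated reason. The plan gives none.

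Safety is part of the primary objective (Section 3.1), and cohorts have 3 to 6 subjects (Section 13.1). At that size, leaving out one treated subject visibly changes a reported incidence. The summary of AEs leading to discontinuation is the most exposed, because subjects who discontinue earliest are the ones removed. Safety rates could also depend on which page of the protocol the analyst used.

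**Working it through.** No figure in the plan needs to be reproduced here. The check compares the two definitions and follows what each does to a subject who stops early.

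**Step 1: who is affected.** The inputs are the dose schedules in Section 4.2, assuming no dose is missed.

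- Level 1, every other day from day 1: doses fall on days 1, 3, 5, 7 and 9, so the fifth dose is on day 9.
- Levels 2 to 4, daily: the fifth dose is on day 5.

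The synopsis rule therefore removes subjects who stop before day 9 at Level 1, or before day 5 at Levels 2 to 4.

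**Step 2: where an early stopper appears if the synopsis rule is applied.**

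| Stops after 1 to 4 doses with | DLT table | AE and SAE summaries |
|---|---|---|
| a DLT | yes (Section 13.2.2) | no |
| an event that is not a DLT | no; subject is replaced (Sections 11.2, 13.2.2) | no |
| no event | no; subject is replaced | not in the denominator |

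Under Section 13.2.1 all three are in the AE and SAE summaries, provided there was one post-dose assessment.

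**Step 3: effect on a reported incidence.** The documents give no rate of stopping before the fifth dose, so the counts below are assumed. In each case one early stopper is replaced. A cohort of *n* evaluable subjects then has *n* + 1 treated subjects.

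- Section 13.2.1 rate = (events in the *n* + event in the early stopper) / (*n* + 1)
- Synopsis rate = (events in the *n*) / *n*

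| Case | Section 13.2.1 | Synopsis | Difference (synopsis minus 13.2.1) |
|---|---|---|---|
| (a) *n* = 6; early stopper has a non-DLT event; one event in another subject | 2/7 = 28.6% | 1/6 = 16.7% | −11.9 points |
| (b) *n* = 6; early stopper has no event; two events in others | 2/7 = 28.6% | 2/6 = 33.3% | +4.8 points |
| (c) *n* = 3; the only event is the early stopper's non-DLT event | 1/4 = 25.0% | 0/3 = 0.0% | −25.0 points |

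These are single examples, not a range. Dropping an early stopper with an event lowers the rate; dropping one without an event raises it. The net direction cannot be stated from the documents.

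**Step 4: what does not depend on the safety population.**

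- DLT counts and escalation use the set in Section 13.2.2.
- AE recording and SAE reporting (Sections 10.3, 10.4.1) have no dose minimum once lenalidomide starts.
- The DISC reviews all adverse events (Section 12.1).
- By-subject listings remain. Section 13.3.1 says: "Physical examination, vital sign, and GVHD data will be listed for each subject at each study visit". It promises no comparable listing of AEs in general, so the AE summaries are the main planned output for those events.

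**The case against.** **The body of the plan is clear.** The synopsis says only that safety variables will be summarised descriptively; it does not restrict the AE tables. The restriction is in Section 13.2.1, directly after the one-dose definition. To omit anyone, an analyst would have to take the restriction from that section and reject the definition beside it. This stands in part: one dose is the more natural reading of Section 13. But the five-dose sentence directly follows the synopsis statement about summarising safety variables, so it is a usable instruction, and no text gives the body precedence.

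**Most early toxicity would still appear as a DLT.** Under item 6 of Section 4.3, a treatment-related effect that causes three or more missed doses is a DLT. A subject who stops for good after four doses misses 11 − 4 = 7 doses of cycle 1 at Level 1, or 21 − 4 = 17 at Levels 2 to 4. Stopping because of a treatment-related effect would therefore normally count as a DLT and be tabulated. This stands as a limit: the group that appears in neither table, and so cases (a) and (c), is mainly subjects who stopped for another reason, such as relapse or withdrawal of consent, and had an unrelated or lower-grade event. Those events still belong in the all-AE and SAE summaries, which are not limited to related events. Subjects with an early DLT would still be missing from the AE tables.

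**The study is descriptive and the counts are invented.** Both points are true. No test or escalation decision changes. The examples show how sensitive a small cohort is, not what will happen.

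**Conclusion.** The concern holds. Two current definitions of one analysis population conflict, and no text resolves the conflict. If the synopsis definition were applied, treated subjects with 1 to 4 doses would drop out of the planned AE and SAE summaries.

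The consequence is conditional on two things: the synopsis rule being used, and at least one subject stopping before the fifth dose. If either fails, the shift is zero. Otherwise one omitted subject can move a cohort incidence by several points or more, in either direction. The timing of the fifth dose assumes no missed doses, and every rate shown rests on assumed counts.

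The point should be corrected because it concerns the analysis set for a primary objective. It does not threaten the MTD determination.

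**What to change.** Replace the synopsis sentence with the Section 13.2.1 definition and a cross-reference. The safety population will comprise "all subjects who received at least one dose of study drug and had at least one post-dose safety assessment" (Section 13.2.1).

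This aligns the synopsis with the section that governs the summaries and with Section 10.3, which requires all AEs to be recorded once lenalidomide starts. No dose, schedule, escalation rule or data collection changes.

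The cost is wording only. Compared with the five-dose rule, the tables may look less favourable if early stoppers had events, or more favourable if they did not.
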